Successful execution of this study will lay the groundwork for a clinical trial to compare the efficacy of a clot-specific imaging modality (**thrombus body scan or TBS**) that has the potential to be more accurate for the diagnosis of VTE, better able to establish the total clot burden in the body with a single test and more widely applicable to patients with renal failure and lung disease.

III. SUBJECT SELECTION

A total of eighty (80) subjects will be recruited for this study, which will be performed at the Massachusetts General Hospital (MGH). All eighty (80) subjects will be studied with the same protocol: a single injection of ⁶⁴Cu-FBP8 and PET-CT imaging at least three hours after injection at four bed positions, which will provide the imaging data for fresh blood clot at the three locations covering all three specific aims.

Inclusion Criteria:

Each subject must meet the following criteria to be enrolled in the study:

- 18 years of age or older with a clinically significant pulmonary embolus (PE) confirmed by a filling defect in CT angiography (CTA), and
- Subjects must receive the radiotracer injection within 72 hours of their diagnosis.

Exclusion Criteria:

- Subjects < 18 years of age
- Time of expected radiotracer injection > 72 hours from the time of a positive venous duplex ultrasound or CT-angiogram,
- Women subjects of childbearing potential who are pregnant, seeking to become pregnant, or have a positive serum pregnancy (beta-HCG) test,
- Unable to lie flat for 45 minutes as assessed by physical examination and medical history (e.g. back pain, arthritis, dyspnea),
- Weight that exceeds the PET camera table limit (300 kg)
- The subject will not be enrolled in the study if the radiation exposure for research studies during the prior 12 months, combined with the exposure from this study would exceed 50 mSv.
- Due to the radiation exposure from imaging studies, all women of childbearing potential will be required to have a negative serum pregnancy test performed prior to any imaging procedures on the same day (if not already done that day). Patients with a positive serum pregnancy test will be excluded. Breast feeding women will also be excluded.
- A pre-existing condition or use of a medication including vasopressors and tPA (due to its effects on clot) that in the opinion of the investigator may place the subject at a substantially increased risk
- Hemodynamic instability, including requiring escalating doses of vasopressor medication.

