- No groups designated as “special vulnerable populations” will be studied.
- No exclusions will be made based on race, sex, or ethnic origin.
- ⁶⁴Cu-FBP8 (Copper-64 labeled fibrin binding probe 8) is cleared by the kidneys, patients with eGFR < 30 will be excluded.

IV. SUBJECT ENROLLMENT

Identification of eligible subjects will be done from 1) admissions to the Massachusetts General Hospital for treatment of pulmonary embolus (PE) 2) admissions to MGH for other indications but with an acute PE at admission or during hospitalization, 3) patients who present to the Emergency Department with an acute PE, but will not be admitted to the hospital. The subjects will be identified through the MGH Pulmonary Embolus Response Team (PERT), radiology notifications or running PeRC Epic team report, which could identify inpatients who were not picked by PERT or radiology notifications, or through patients physician investigators may be aware of that have an acute PE. PERT is a well-established group of cardiologists, pulmonologists, interventional radiologists, emergency room physicians, and cardiac surgeons who are “on-call” when a clinician anywhere in the hospital suspects a patient has a clinically significant pulmonary embolus. When PERT is activated, a fellow organizes a web-based meeting within minutes through a page and email to the participating physicians. The data is reviewed via “go-to-meeting” conference and a treatment plan is decided upon by consensus. An email will be sent to [name], and [name] when PERT is activated and [name] will assess whether the patient is appropriate and potentially eligible for the study. Also, since the fibrin probe must be manufactured at MGH Navy Yard and sent to MGH main campus, only patients diagnosed at a time when they can receive the radiotracer within 72 hours of their diagnosis will be included. If the patient meets eligibility criteria, the patient’s treating physician will be contacted to ask the patient for permission to be contacted by the study staff. During the first contact, the physician co-investigator will screen the subject for eligibility and describe the study and its implications, risks and benefits. If the subject is interested, the consent form will be given to the subject to read. The subject will be given as much time as necessary to decide, however if a decision cannot be made within the 72-hour limit from initial diagnostic imaging to the fibrin probe injection, or not before a scheduling time window for fibrin injection, the subject will be excluded. We will allow as much time as necessary for the subject’s questions to be answered or for the subject to consult family members or treating doctors before the consent form is signed. After the subject signs the consent form, the original signed consent form will be kept on file, a copy will be given to the subject, and a copy will be scanned to the subject EMR. No study procedures will be performed prior to the subject signing the informed consent document. The informed consent process will be accurately documented in the subject medical records.

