On the day of PET-CT imaging, an intravenous catheter will be placed if there is not one already in place that can be used in the case of subjects admitted to the hospital. All women of childbearing potential will be tested for pregnancy unless a test result is available in the medical record that is valid for the day of PET-CT imaging. Women who are documented by medical history of not having child-bearing potential (i.e. tubal ligation or hysterectomy) or are post-menopausal with a minimum one year without menses will not need to undergo pregnancy testing. A STAT quantitative serum hCG pregnancy test will be performed on the day of the scan. Blood samples (up to 8 ml total) will be drawn for pregnancy test, coagulation panel (PT, PTT, INR), platelets and D-dimer if not already done that day by the clinical team. If the test performed comes back negative for pregnancy (<6 IU/L), the subject will be enrolled. If the test performed comes back positive for pregnancy the subject will not be enrolled in the study. Blood samples will be taken via indwelling catheters already present for hospitalized patients. If the subject’s intravenous access is unable to be used, a new peripheral intravenous catheter will be placed by study staff to draw the required blood for beta-HCG (if required), D-dimer and

administer the radiopharmaceutical. For subjects coming for PET-CT as an outpatient an intravenous catheter will be placed to allow for obtaining blood samples and radiopharmaceutical administration.

Once finished, arrangements will be made to conduct the PET-CT imaging in a way that does not interfere with treatment for subjects admitted to the hospital.

Prior to radiotracer injection for PET imaging:

- The procedure will be explained to the subject and any questions he/she has about the procedure will be answered.
- Subject information such as height and weight will be obtained if not available.
- Vitals and ECG will be obtained prior to radiotracer injection.

Radiotracer injection:

- Up to 10 mCi ⁶⁴Cu-FBP8 will be injected at least 3 hours before the scheduled time for PET-CT imaging. The injected dose and time of injection will be recorded. The injection will take place at the bed side.
- The catheter will be flushed post-injection of ⁶⁴Cu-FBP8 with 10ml 0.9% saline solution.
- Vitals will be obtained immediately after radiotracer injection.

PET-CT imaging:

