- For subjects admitted to the hospital close to the scheduled time for imaging, which is at least 3 hours after injection, the subject will be escorted (transported) in the wheelchair or stretcher/bed by hospital transport and/or study staff depending on the subject conditions to the PET-CT suite; we will follow the hospital standard procedures for patient transport. The PET-CT technician will submit a patient transport order through Epic. When the PET suite becomes available, the hospital transport team will transport to the PET-CT location. If the subjects need to be monitored during the transport, then one of the study physicians will be present during the transport.
- Subjects coming as outpatient will come to the hospital (Anesthesia or Pulmonary Research area) at least 4 hours prior to the imaging where they will be injected and monitored before taking them to the PET-CT imaging suite.
- Prior to the scan subjects will be asked to urinate to minimize the possibility that they will need to move during the scan.
- The subjects will be positioned on the scanner table; support devices under the back and/or legs will be used as needed to enable the patient to comfortably maintain his/her position throughout the scan.
- A scout image (Topogram) which takes about 10 seconds will be obtained to locate the proper fields for imaging.
- Afterwards, CT and PET scans will be obtained for four bed positions: thorax, pelvis and thighs (2 positions). The CT scan for each position of the PET scans is necessary to correct for the attenuation of the ⁶⁴Cu-FBP8 activity caused by body tissue. We will perform an additional PET/CT scan of the lower portion of the thighs in order to image the full/whole thighs to the knees. Consequently, a total of 4 CT and 4 PET scans will be performed in four different positions. Imaging duration will be less than 10 seconds for each CT, and 10 minutes for each PET scan. The total time of imaging is expected to be approximately 45 minutes.
- We may have to repeat a PET-CT scan if we have an unexpected problem (for example, if subjects need to change position during a scan).
- Subjects will be monitored throughout the imaging session, and measurements including heart rate, blood pressure, and pulse oximetry will be recorded.

Post-scan procedures:

- After the scans are completed and last vital signs collected, the subject will be escorted back to his/her room on the ward if applicable

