Patients will be contacted at 3, 6 and 12 months following the diagnosis of PE. Death and recurrence of DVT-PE will be assessed. Results of any imaging studies (CT angiograms, echocardiograms, or venous duplex ultrasound studies) and serologic studies (follow up d-dimer) will be collected and patients will undergo a survey to collect information about symptoms attributable to PE-DVT as well as quality of life using Standard Form 36,²⁸ VEINES QOL29 and the patient's self-assessment of their overall health status on a 1 – 10 scale, with 1 indicating the worst possible and 10 the best possible health. For patients followed at MGH this will be done in person at the end of their PERT or pulmonary clinic follow up clinic visit. For those followed elsewhere, this will be done by telephone with subjects and their treating physicians. NYHA functional class, 6-min walk distance, and change in pulse oximetry with walking will be assessed.

VI. BIOSTATISTICAL ANALYSIS

Once a patient is enrolled, the subjects will receive an injection of up to 10 mCi ⁶⁴Cu-FBP8 and imaged with CT-PET approximately at least 3 hours after injection, when the “target-to-background” ratio (TBR) of activity is expected to be high based on previous studies.²⁷ With CT-PET the attenuation correction is done using a low-dose CT volumetric scan. Afterwards, PET acquisitions of 10 min duration each are performed in four positions, thorax, pelvis and thighs (2 positions), which are used to assess regional ⁶⁴Cu-FBP8 activity.

Specific data variables:

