The standardized uptake value (SUV) of ⁶⁴Cu-FBP8 uptake in the lungs, pelvis and thighs will be calculated. The target to background ratio (TBR) for ⁶⁴Cu-FBP8 activity will be calculated using as background a region of interest (ROI) created from large cardiac and vascular structures. This corrects the ⁶⁴Cu-FBP8 activity for differences in injected dose and timing of imaging and allows for flexibility in the image timing. One member of our group ([name]) and another from Nuclear Medicine ([name]) will be blinded to the clinical results and will identify the presence or absence of clot in the three imaged locations as well as the anatomic location(s) and extent as best as possible from the overlay of the fibrin activity on the attenuation correction CT scans. Additionally, we will perform quantitative image analyses including the volume of the thrombus ROI, activity of imaged clot in each imaged section and clot burden. The thrombus ROI is defined by a threshold of 50% between peak activity of the ROI and background activity. Multiple ROIs will be used in the case of separated thrombi. Clot burden will be estimated using the sum of ⁶⁴Cu-FBP8 activity within a thrombus ROI and then normalized by the injected dose.

Outcome Measures:

Specific Aim 1: The location and extent of the thrombus region of interest (ROI), its volume and clot burden within the lung ROI will be compared with the ROI of filling defects on CT-angiogram. We will determine the number and location of the thrombus ROI(s) within the lungs, and the overall clot burden as sum of ^{64}Cu -FBP8 activity within a thrombus ROI(s) within the lungs. Additionally, we will calculate the intersection of the thrombus ROI and filling defects ROI relative to volume of the thrombus ROI. That will quantify the fraction of thrombus ROI(s) using a scale from being are completely outside (0) to completely inside (1). Also, we will perform a lung segmentation using the software APOLLO (VIDA Diagnostics) and determine in which lung lobe the thrombus ROI(s) are located.

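### The plan treats the target-to-background ratio as correcting for scan timing; it cannot remove biological clearance, and the between-subject D-dimer and outcome analyses have no adjustment for scan delay or renal function

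*Combined protocol and SAP*

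**What the plan says.** Section VI (Specific data variables) defines TBR with a background "region of interest (ROI) created from large cardiac and vascular structures", which is in effect the blood pool, and then states: "This corrects the ⁶⁴Cu-FBP8 activity for differences in injected dose and timing of imaging and allows for flexibility in the image timing".

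Every statement of the interval is a minimum. Section III has "PET-CT imaging at least three hours after injection at four bed positions"; Section V (Radiotracer injection) says the probe "will be injected at least 3 hours before the scheduled time for PET-CT imaging"; the opening of Section VI has "approximately at least 3 hours after injection, when the “target-to-background” ratio (TBR) of activity is expected to be high based on previous studies". No maximum or target window is given. The 72-hour limit runs from diagnosis to injection, not from injection to scan. For inpatients, Section V adds: "When the PET suite becomes available, the hospital transport team will transport to the PET-CT location". Outpatients arrive at least 4 hours ahead of imaging, again with no upper limit.

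On clearance, the exclusion criteria say "⁶⁴Cu-FBP8 (Copper-64 labeled fibrin binding probe 8) is cleared by the kidneys" and bar eGFR below 30, so subjects from 30 upward are enrolled. On data capture, Section V says "The injected dose and time of injection will be recorded". Scan start time is not listed, and creatinine is collected where available.

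Section VI (Outcome Measures) divides clot burden and total activity by injected dose. For Aim 3, total activity in the imaged fields leaves out the kidneys, bladder, liver and gallbladder, but not the heart and great vessels, and is correlated with D-dimer. For all aims, clot burden is compared with mortality, recurrent VTE and quality of life, stratified by treatment. Neither delay nor renal function enters any analysis.

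**The concern.** The sentence claims a property that the ratio does not have, and uses it to justify a free interval. As unbound probe leaves the blood, the denominator falls. Unless the clot signal falls in step, the same clot gives a different TBR at a different delay.

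The analyses that compare subjects do not even use the ratio. They use activity divided by injected dose, so whatever protection TBR gives does not reach them. Total activity is the most exposed: with blood pool left in, circulating unbound probe is counted as fibrin activity. That part depends on the delay and on how fast the subject clears the probe.

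Section I says that renal dysfunction is common in older patients and that D-dimer discriminates less well in them. Age is therefore a plausible common factor behind retained activity and D-dimer, and could create or distort a correlation for reasons other than clot.

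**Working it through.** The documents give no TBR value, kinetic constant or power calculation, so there is no figure to reproduce. The check is algebra plus a range over assumed half-lives.

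**1. What the ratio cancels.** Let D be injected dose, λ physical decay, u and b initial uptake in clot and blood, and k_c and k_b their biological washout rates.

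- Clot: D·e^(−λt)·u·e^(−k_c·t)
- Blood: D·e^(−λt)·b·e^(−k_b·t)
- TBR(t) = (u/b)·e^((k_b − k_c)·t)

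D and λ drop out. Time drops out only if k_b = k_c, or if both are near zero by the time of scanning.

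**2. What the documents say about k_b and k_c.** Section I reports high target uptake and low background retention in rats. Section VI waits 3 hours because TBR should then be high. Both suggest a ratio that rises for some period after injection. Neither says whether it is still rising after 3 hours.

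**3. Effect of moving a scan from 3 to 6 hours.** The half-lives h are assumptions. With stable clot, the TBR factor is 2^(3/h). With clot washing out at half the blood rate, it is 2^(1.5/h). The blood-pool part of decay-corrected total activity is multiplied by 2^(−3/h).

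| Assumed blood half-life h | TBR factor, stable clot | TBR factor, clot at half the blood rate | Blood-pool activity, 6 h relative to 3 h |
|---|---|---|---|
| 2 h | 2.83 | 1.68 | 0.35 |
| 3 h | 2.00 | 1.41 | 0.50 |
| 6 h | 1.41 | 1.19 | 0.71 |
| 12 h | 1.19 | 1.09 | 0.84 |
| Plateau | 1.00 | 1.00 | 1.00 |

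The last column is what matters for the D-dimer correlation. Its effect on total activity depends on the share of that total lying in blood, which the documents do not give.

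**4. Effect of renal function at a fixed 3 hours.** Assume a stable clot signal and a renal share f of clearance that is proportional to eGFR. At eGFR 30 the rate is k_b·(1 − f + f/3), so TBR at eGFR 90 relative to eGFR 30 is 2^(2f/h), with h the half-life at eGFR 90. For h of 2, 4, 8 and 16 hours:

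- f = 1: 2.00, 1.41, 1.19, 1.09
- f = 0.5: 1.41, 1.19, 1.09, 1.04

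**5. Clot burden.** If the clot signal is stable and decay-corrected, delay reaches clot burden mainly through the ROI boundary. A threshold halfway between peak P and background B lies at (P + B)/2, so it moves with B.

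**6. Decay correction.** If activity were not corrected to injection time, an assumed ⁶⁴Cu half-life of 12.7 h leaves 0.5^(3/12.7) = 0.849 at 3 h and 0.5^(6/12.7) = 0.721 at 6 h, a ratio of 0.85. Assumed half-lives of 10 to 15 h give ratios of 0.81 to 0.87.

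**The case against.** Much of the case on the other side stands.

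- A reader might infer that TBR drift undermines all three aims. It does not. TBR is listed as a data variable but appears in no named comparison. Aims 1 and 2 set PET against CT angiography or ultrasound in the same patient, with two blinded readers. Delay could affect how visible a clot is, but drift between subjects does not directly confound those comparisons.
- A reader might take the 3-hour wait as an admission that TBR keeps changing. A ratio expected to be high from 3 hours is also compatible with a plateau. The citation there is to the EP-2104R MRI study, but Section VII explains the kinship of the two agents and reports 37 subjects imaged with this probe. The investigators may hold data that settle the matter; the documents do not show them.
- A reader might infer that activity is not decay-corrected and drifts by about 15%. The plan calculates SUV and uses the scanner manufacturer's reconstruction, which may well supply the correction. The text is silent, so this needs confirming and is not a shown defect.
- A reader might infer that inpatients are systematically scanned later than outpatients. Section V ties injection and inpatient transport to a scheduled imaging time, and the outpatient wording has no ceiling either. A systematic difference is conjecture.
- A reader might state as fact that low eGFR lowers TBR. No kinetics by eGFR are given, and slower clearance also exposes the clot to probe for longer, which could raise the numerator.

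None of this rescues the sentence itself, nor the absence of any adjustment in the between-subject analyses.

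**Conclusion.** The concern holds in a limited form. The stated correction for timing is wrong as a general property of the ratio: it holds only under equal washout or plateau. The consequence falls mainly on the between-subject analyses, first the secondary D-dimer correlation with total activity, then the comparisons of clot burden with clinical outcomes. If the undefined high-activity criterion in Aim 3 were set on TBR, it would be affected too.

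The algebra is firm; the size is not. Every factor above rests on assumed half-lives, an illustrative 3-hour slip and an assumed clot washout, and the range runs from no effect to nearly threefold. The point merits a change to the analysis plan, but does not call the within-patient comparisons into question.

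**What to change.** 1. In Section VI, limit the sentence on TBR to injected dose and physical decay.
2. State that clot burden and total activity are decay-corrected to injection time, or add that step.
3. Record scan start time alongside injection time.
4. Include the injection-to-scan interval and eGFR as covariates in the D-dimer and outcome analyses and in any between-subject use of TBR. At the least, pre-state a sensitivity analysis that does so.
5. Report the distribution of the interval.

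Injection time is already recorded and eGFR is needed for eligibility, so the only new data item is scan start time. The analytic cost is two extra covariates in an 80-subject study. If deaths or recurrences are few, the sensitivity analysis is the more workable route for those outcomes. No imaging window is proposed; that choice rests with the investigators.

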Our long-term research objective of this translational study is to establish a novel thrombus body scan (TBS) using a new fibrin-specific probe for positron emission tomography (PET) imaging to overcome the limitations of indirect VTE diagnosis, and, with one single test, provide a total-body assessment of fresh intravascular clot.

Scheme 1. Simplified synthetic route and chemical structure of ^{64}Cu -FBP8. The sequence of the core fibrin-binding peptide is reported on the bottom.

II. SPECIFIC AIMS

This proposal aims to generate strong evidence for VTE diagnosis using the thrombus body scan (TBS) from an initial small translational study that will justify a larger clinical study to obtain clinical approval for the TBS. We hypothesize that TBS using our new PET fibrin probe that specifically binds to fresh polymerized fibrin clot (< 1 week old), can directly detect thrombus anywhere in the body similar to ^{18}F -FDG PET scans for cancer nodules, will have better diagnostic accuracy for deep venous thrombosis and pulmonary embolus (DVT-PE) compared to current imaging modalities, can quantify the total body burden of fresh clot and can be performed in patients with renal dysfunction. Before we can fully test this hypothesis in an appropriately-powered clinical study, we propose a proof-of-concept study in a smaller cohort of patients to test the following specific aims and hypotheses:

1. Compare the presence, location and extent of PE diagnosed with the PET ⁶⁴Cu-FBP8 probe to conventional imaging. *Hypothesis:* The PET fibrin probe will allow direct imaging of acute thrombi causing PE, which is currently only indirectly diagnosed by filling defects on CT-angiogram or mismatched perfusion defects on V-Q scans.

2. Compare the presence, location and extent of DVT diagnosed with the PET ⁶⁴Cu-FBP8 probe to conventional imaging. *Hypothesis:* The PET fibrin probe will allow direct imaging of acute thrombi causing DVT diagnosed indirectly by incompressibility and loss of flow on lower extremity venous Doppler ultrasound.

3. In addition to PE and lower extremity DVT, assess for upper extremity and pelvic clot and compare the extent of total body clot burden imaged with the ⁶⁴Cu-FBP8 probe to the plasma D-dimer level. *Hypothesis:* The PET fibrin probe will discover acute thrombi including areas not assessed by current imaging methods and the total clot burden will correlate with the plasma D-dimer.

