- The subject will be asked to void again immediately after the scan, and he/she will be counseled on the importance of continuing to drink fluids for several more hours. This will increase urine flow rate, which will help minimize the radiation dose to the bladder wall.

Data acquisition and image reconstruction:

PET-CT images will be acquired using commercial, FDA-approved scanners using conventional sequences for image acquisition. Images will be reconstructed using the algorithms provided by the scanner manufacturer. All images will be completely anonymized and de-identified and labeled only with a study number. No personal information whatsoever will be contained in the images or header files. The images will be transferred electronically over a secure internal network to the storage site at the Pulmonary and Bioengineering Laboratory, where they are securely stored and backed-up. Only study staff will have the required permissions and ability to access these files.

A separate database file, linking the study number to the relevant clinical data on each subject will be generated. These data will be stored in a password-protected Redcap (Research Electronic Data Capture) database supported by the Massachusetts General Hospital and Partners Healthcare. Only study staff involved in data collection and analysis will have access to this database. For this study, we will record basic demographic data (age, gender, race/ethnicity), and clinical data (results of laboratory values such as serum creatinine, D-dimer and NT-pro-BNP, results of CT-angiogram, including de-identified DICOM files, results of venous duplex ultrasound, echocardiographic parameters of cardiac size/function/hemodynamics, and treatment, height, weight and baseline hemodynamics and hospital mortality), as available. Additionally, images will be stored for data analysis on a password protected file server at the Pulmonary Imaging and Bioengineering Laboratory at Massachusetts General Hospital, and access will be restricted to study staff involved in data analysis.

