Specific Aim 2: The thrombus ROI, its volume and clot burden within the thigh ROI will be compared with the location and extent of the clot on venous duplex ultrasound. We will determine the number and location of the thrombus ROI(s) within the thigh ROI, and the overall clot burden as sum of ^{64}Cu -FBP8 activity within a thrombus ROI(s) within the thigh ROI. Additionally, we will quantify the volumes and locations of the thrombus ROIs of the PET scan and the venous duplex ultrasound relative to each other. Also, we will perform a vessel segmentation using the 3D Slicer (open source software) and determine the location of thrombus ROI(s) with the blood vessel.

Specific Aim 3: The prevalence of high ^{64}Cu -FBP8 fibrin activity in the pelvic ROI and upper extremity ROI's will be reported. Additionally, as a secondary analysis, both the total fibrin activity in the imaged fields, excluding the liver, gallbladder, kidneys and urinary bladder normalized by injected dose for all patients will be correlated with the plasma D-dimer drawn at the time of imaging. D-dimer levels will be drawn daily from the time of first diagnostic imaging to the fibrin probe imaging (up to 3 days maximum in total) as well as PT, PTT, platelets and fibrinogen. Anticoagulants used, as well as timing and dose will be carefully recorded during this period.

For all Specific Aims, death, VTE recurrence, and quality of life measures will be compared with the clot burden measured by PET and conventional imaging modalities, stratified by treatment (systemic thrombolysis, catheter thrombolysis, or heparin alone) using multiple correlation, ANOVA, and t-tests for pairwise comparisons.

VII. RISKS AND DISCOMFORTS

^{64}Cu -FBP8 PET probe:

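### Aim 1's only defined PET-CTA overlap score cannot register CTA-visible clot that PET misses, and it is undefined when PET shows no clot

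*Combined protocol and SAP*

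**What the plan says.** Aim 1 (Section II) reads "Compare the presence, location and extent of PE diagnosed with the PET" probe, set against conventional imaging. The inclusion criteria (Section III) require a PE confirmed by a CTA filling defect, so every subject has CTA-visible clot by design.

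Section VI, Outcome Measures, Specific Aim 1, contains:

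- A general comparison. The PET thrombus region's location and extent, "its volume and clot burden within the lung ROI will be compared with the ROI of filling defects on CT-angiogram". No statistic is named.
- The number, lung location and summed activity of the PET regions, with a lobe assigned to each PET region. Neither a count nor a lobe assignment is stated for the CTA defects.
- As an additional item, the one overlap statistic with a formula: "we will calculate the intersection of the thrombus ROI and filling defects ROI relative to volume of the thrombus ROI". It is scored 0 when the PET region lies wholly outside the defects and 1 when it lies wholly within them.

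Two other places bear on the point. Under Specific data variables in Section VI, two blinded readers "will identify the presence or absence of clot in the three imaged locations as well as the anatomic location(s) and extent". At the end of Outcome Measures, death, recurrence and quality of life are to be compared with "clot burden measured by PET and conventional imaging modalities". Neither names a measure with the CTA filling defect as its denominator. No rule is given for a subject with no PET region in the lung.

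**The concern.** An overlap between two regions can be divided by either volume, and the two ratios answer different questions. Dividing by the PET volume asks whether the PET signal sits where CTA shows a defect. Dividing by the CTA volume asks how much of the CTA-visible clot PET found. The plan defines only the first.

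In a cohort made up entirely of CTA-positive patients, the second question bears most directly on the extent part of Aim 1. The study is also meant to justify a larger one (Section II). An overlap figure near 1.00 would be read as good agreement, yet it can occur when most of the CTA clot is unseen on PET. Subjects with no PET region have no score. If they simply drop out of the summary, the complete misses are the cases removed.

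**Working it through.** The documents give no expected overlap, precision or power figure, so there is nothing to reproduce. The check is algebra on the plan's own definition.

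**Notation.** P is the PET thrombus region volume, F the CTA filling-defect volume and I the volume of their intersection. By the inclusion criterion F > 0; P can be 0.

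- Planned score: s = I / P
- CTA-side coverage (not in the plan): c = I / F
- Dice (not in the plan, optional): D = 2I / (P + F)

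Set F = 1 and P = r. Then s = I / r, c = I and D = 2I / (r + 1). It follows that c = s × r, that is, coverage = planned score × V(PET)/V(CTA). Neither factor alone determines coverage.

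**Partial detection.** Take four equal emboli, k of them found, with the PET regions inside the defects, so r = I = k/4.

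| k found | s = I/r | c = I | D = 2I/(r+1) |
|---|---|---|---|
| 4 | 1.00 | 1.00 | 1.00 |
| 3 | 0.75/0.75 = 1.00 | 0.75 | 1.50/1.75 = 0.86 |
| 2 | 0.50/0.50 = 1.00 | 0.50 | 1.00/1.50 = 0.67 |
| 1 | 0.25/0.25 = 1.00 | 0.25 | 0.50/1.25 = 0.40 |
| 0 | 0/0, undefined | 0 | 0 |

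**The reverse case.** If all clot is found but half the PET volume lies outside the defects, then r = 2 and I = 1, so s = 0.50 and c = 1.00. The planned score falls although nothing was missed.

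**Does a volume comparison fill the gap?** Take equal volumes, r = 1. With I = 0, 0.5 or 1, the volume ratio is 1.00 each time while c = 0, 0.50 or 1.00. It does not.

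**Effect on a group summary (illustrative).** The documents give no rate of scans without a PET lung region. Assume 5%, 10%, 20% or 40% of the 80 subjects have none, and that all other PET regions lie inside the defects. The score is then undefined for 4, 8, 16 or 32 subjects, and its mean over the rest is 1.00 in every case. Mean coverage over all 80 would be 76/80 = 0.95, 72/80 = 0.90, 64/80 = 0.80 or 48/80 = 0.60 if the other subjects' clot is fully covered. It would be half of each (0.475, 0.45, 0.40 or 0.30) if their clot is half covered.

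**The case against.** The strongest reply is that the score is a secondary descriptive item and the plan does not rely on it alone. The leading Aim 1 outcome compares PET location, extent, volume and burden with the filling-defect region. Since coverage equals score times volume ratio, reading the two together would separate every case above. The filling-defect region has to be drawn for the intersection anyway, so no data are lost. This is correct, and it is why the fix is cheap. But combining the two is the step the plan does not state, and the general comparison names no statistic.

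Second, the plan does not say whether the score is pooled per patient or computed per PET region. If per region, one embolus found gives one score and four found give four. Even so, each score is 1.00, and the planned count of PET regions has no stated CTA count to set it against.

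Third, a lung without PET signal would be recorded by the blinded readers, and its count, volume and burden would be zero. That stands: a complete miss would be visible elsewhere. The share of clot missed in a partial miss would not be, and the score still lacks a reporting rule.

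Fourth, low coverage is not proof of PET error. The probe is said to bind clot less than a week old, the Background says filling-defect imaging can hardly separate old clot from new, and up to 72 hours may pass between diagnosis and injection. This also stands. It is a reason to report coverage with a caveat; the planned score cannot show this discordance at all.

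Finally, no test, threshold or go/no-go rule depends on the score. That limits the severity to an incomplete analysis.

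**Conclusion.** The point holds and should be fixed. The only overlap statistic defined for Aim 1 is insensitive to CTA-visible clot that PET misses: it stays at 1.00 while coverage falls from 1.00 to 0.25 in the four-embolus example. It does not exist for a subject with no PET region. No CTA-side measure is named anywhere in the plan.

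The algebra needs no assumed study data. The embolus counts and volumes are illustrations, and the PET-negative shares are assumptions. The score is valid for its own question, whether PET signal falls inside CTA defects, and the rest of Aim 1 is not invalidated. What is missing is the complementary measure and a rule for subjects without a PET region.

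**What to change.** 1. Keep the planned score for subjects with a PET lung region, and report how many subjects have none.
2. Prespecify V(PET and CTA)/V(CTA filling defect), set to 0 when there is no PET region, for all subjects with an evaluable CTA file. Report how many lack such a file. Dice is optional.
3. Describe patient-level lung results as a detection rate in CTA-positive patients. State that low coverage may reflect old clot, lysis or change between the scans, and not only PET error.
4. Optionally, and descriptively only, assign the CTA defects to the same lobes as the PET regions and report the lobe-level PET-by-CTA table with intervals that allow for clustering within patients.

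Items 1 to 3 cost SAP wording and a little analysis time, with no new scan or visit. The planned intersection already needs both regions in one frame, so coverage adds only the filling-defect volume. Section V (Data acquisition) lists "results of CT-angiogram, including de-identified DICOM files" within a list that ends "baseline hemodynamics and hospital mortality), as available", so some subjects may not be evaluable; the planned score has the same limit. Item 4 costs more, because the plan does not say which CT is segmented into lobes and registration may be needed. The downside is that the overlap figures may look less favourable and must be read with the caveat in item 3.
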